A sub-study of patients will receive vulvar biopsies at baseline and again after the 3-month intervention. A total of 20 paired biopsies (one at baseline and one after the 3-month intervention) will complete this substudy. The number has been estimated using a power analysis based on our previous histopathologic findings (see section 12). Subjects completing both biopsies will be remunerated with \$100. If a subject only completes the baseline biopsy she will not count toward the total as the before and after intervention analysis of the biopsy samples is critical. As such, more than 20 women may enroll in the sub-study, but if any participants discontinue prior to the post-intervention biopsy they will be replaced so a total of 20 paired biopsies will be collected.

Reference patients will be 5 women who are not using estrogen supplements and do not have dyspareunia. They will be recruited from an OHSU urogynecology study of postmenopausal women who have urinary complaints and control women who do not. Among those screened or who have finished the study, we anticipate being able to approach women who are not using estrogen products but who have no urinary complaints and no dyspareunia. We would ask them to fill out the entry questionnaire and have a 4mm mucosal biopsy in the right or left vestibule adjacent to a Bartholin's duct orifice. This is the equivalent location of worst tenderness in women with localized provoked vestibulodynia of postmenopause. Subjects who agree to a biopsy will be remunerated with \$100.

Inclusion and Exclusion Criteria

Potential subjects will first be screened during a phone conversation with the Women's Health Research Unit (WHRU) recruitment coordinator or study staff (see phone screen form). After pre-screening eligibility is confirmed, if subjects want to screen for study participation they will be scheduled to be seen in the WHRU clinic with the study coordinator and study clinician.

In the event of screen failure, data collected by phone and at screening will be retained for separate analysis.

Inclusion Criteria

- 1. Postmenopausal women aged at least 40 years old.
- 2. Postmenopausal, defined by at least one of the following:
 - i. Amenorrhea ≥1 year in women > age 50 with a previously functioning uterus and presence of 1 ovary
 - ii. Bilateral oophorectomy
 - iii. FSH >30 in women with at least 1 ovary who are age 40-50 with >1 year amenorrhea

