 - iv. A history of peak menopausal symptoms >2 year prior in women age>51 with no functioning uterus (previous ablation or hysterectomy)
 - v. FSH >40 in women of age >51 if they have no prior history of classic menopausal symptoms (hot flashes, night sweats) and have 1 ovary but amenorrhea that was surgically induced (by ablation or hysterectomy)
- 3. Onset of dyspareunia after menopause but not before.*
- 4. Stable heterosexual partnership ≥1 years (or by investigator discretion if less than 1 years) and both partners want to have more satisfying penetrative intimacy.
- 5. No estrogen product use, local or systemic, for 6 months.
- 6. More than 6 months of consistent insertional pain with intercourse (may have stopped having intercourse due to this consistent experience of pain).*
- 7. Willingness to enter a study where she will receive low-dose local estrogen.*
- 8. Willingness to enter a study that requires application of cream on a frequent schedule for 3 months. *
- 9. Willingness to evaluate the progress of therapies by use of the Tampon Test as many as 2 times per week, and willingness to attempt intercourse if the Tampon Test indicates tolerable penetrative pain.*

Exclusion Criteria

- 1. Consistently has pain in the pelvis or low abdomen (chronic pelvic pain)
- 2. Negative cotton-swab touch test in the vulvar vestibule* or vestibular tenderness that is not extinguishable by application of lidocaine 4% topical solution applied for 3 minutes.
- 3. Partner with sexual dysfunction limiting his performance or making it inconsistent. (The use of male therapy for erectile dysfunction is acceptable.)
- 4. Diagnosis by a physical therapist or clinician of significant pelvic floor muscle tension causing pain (pelvic floor myalgia) or has been found on screening examination to have pelvic floor tenderness or bladder tenderness.
- 5. Constant burning pain localized to the vulva.
- 6. Allergy to local estrogen products or lidocaine numbing agents.*
- 7. Previous estrogen receptor positive breast cancer or endometrial cancer or has been cautioned about estrogen because of any other cancer
- 8. Endometrial thickness ≥5mm on screening via transvaginal ultrasound.
- 9. Vulvovaginitis assessed at screening exam.

^{*}n/a for reference group

^{*}n/a for reference group

Vulnerable Populations

This study will not include special populations. The criteria for the intended population will exclude groups designated as special populations.

Setting

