Subjects who do not speak English will not be enrolled.

9. Procedures Involved

This study includes up to 7 visits as outlined below:

Visit 1 (Screening Visit)

- Consent
- Review of inclusion/exclusion criteria
- Medical/surgical and medication history
- Pelvic examination to assess genital atrophy and vestibule tenderness

- Vestibule tenderness assessment will include the cotton-swab touch test (a test of mucosal sensitivity) and the lidocaine test (application of 4% aqueous lidocaine to tender mucosa for 3 minutes with reassessment of the cotton swab test to assess by what percentage the mucosal pain has been extinguished).
- The initial cotton swab used to map the tenderness in the vestibule and one from a vaginal side wall sample will be labeled, frozen and stored for later batched analysis of the microbiome composition.
- Transvaginal ultrasound to assess endometrial stripe thickness
 - Since subjects will have been selected because of having pain with vaginal penetration, it will be assumed that the vaginal probe used for the ultrasound examination will not be comfortable for the subject to insert without some preventative treatment. The study clinician will pre-treat the location of tenderness with 4% aqueous lidocaine for several minutes prior to insertion of the vaginal probe. This should prevent or minimize local pain from the vaginal probe.
- Blood sample collection for serum β-estradiol
- Completion of questionnaires
 - Demographics
 - Vulvar Pain Assessment Questionnaire (VPAQ), modified, #1
 - Lower Urinary Tract Symptoms (LUTS) questionnaire
- Randomization to study drug by Research Pharmacy, after all eligibility criteria confirmed by study staff
- Vulvar biopsy (for those subjects enrolling in the sub-study)
 - If participant agrees to biopsy, the baseline sample can be collected at either V1 or V2, dependent on subject preference
 - 4mm vestibule punch biopsy at the 4 or 8 o'clock site next to one of the Bartholin duct orifices after the zone has been pretreated with topical 5% lidocaine ointment for 10 minutes

Visit 2 (Enrollment/Randomization) - ***THIS VISIT MAY BE COMBINED WITH VISIT 1***

- Confirmation of inclusion/exclusion criteria
- Update to medical and medication history
- Dispensing of study drug with review of how to use/apply by study staff
- Dispensing of diary forms and review of instructions for documentation
- Dispensing of Tampons

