Participation for reference group subjects will last the duration of Visit 1. There will be no follow up of reference subjects.

Genetic Testing:

No human genetic testing or collection of human genetic information is involved in this study. Ribosomal RNA will be analyzed from resident vaginal and vestibular microbes.

10. Study Drug

The study drug will be compounded β -estradiol, an FDA approved medication. It will be compounded by Lloyd Center Pharmacy, which has a long history of collaboration with the OHSU Research Pharmacy. They adhere to the standards of the US Pharmacopeial Convention (USP), a 194 year-old scientific organization that sets standards for medication purity; in the US the FDA enforces these standards. Lloyd's adheres to Chapters 797 (sterile medications) and 795 (non-sterile medications) of the USP, and the β -estradiol cream, being a non-sterile product, will adhere to standards set out in Chapter 795.

Subjects will be randomized to receive one of two strengths of compounded β -estradiol cream: 100mcg or 50mcg/0.5 gram. Each subject will be issued a pump that will dispense 0.5cc (0.5gm) of study drug with each pump action. They will be instructed in application of the cream to the vulvar vestibule on a nightly basis. They will be asked to keep a diary record of drug applications.

The β -estradiol cream will be twice the strength of the recommended FDA-approved strength so as to be able to dose half the amount for purposes of patient acceptability. Too much cream would likely elicit complaints of messiness and excess discharge. The base study cream will be Versabase, a well-known and well-absorbed base for compounded vaginal medications. It is free of propylene glycol, a preservative found in the base used in the proprietary vaginal creams, known to be an irritant to the vestibule.

Subjects, investigators and personnel will be blinded as to the randomization, as the OHSU research pharmacy will make the assignments. We will request that subjects bring remaining study medication to their final study visit (Visit 6) for collection by study staff so dosing may be confirmed after analysis, if needed.

11. Data and Specimens

a. Handling of Data and Specimens

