Confidentiality of personal health information will be maintained according to HIPAA requirements for research. All subjects will receive a study number to which all subsequent data will refer. Personal identifiers will not be on questionnaires, data, abstract sheets, or in the main database. All data will be kept in locked files or a password protected computer in the Principal Investigator's (PI) office. We will do our best to keep information confidential by keeping it coded and on password-protected computer.

14. Provisions to Monitor the Data to Ensure the Safety of Subjects

See Data Safety Monitoring Plan (DSMP) document.

15. Risks and Benefits

a. Risks to Subjects

Risks to subjects include:

- Breach of confidentiality
 - We will do our best to avoid this risk as outlined above and in the DSMP
- Inconvenience of coming in for several visits
- Inconvenience of keeping a study diary
- Psychological discomfort from filling out questionnaires to assess pain and distress
- Psychological stressors related to a study which focuses on sexual function and pain since these issues may have created stresses in their relationship
- Discomfort of ultrasound
 - There are no known harmful effects of transvaginal ultrasound.
 Women may experience vaginal discomfort which we plan to minimize with the use of 4% aqueous lidocaine for several minutes prior to insertion of the vaginal probe
- Discomfort from blood draw
 - Women may feel some pain when their blood is drawn by venipuncture, but there is minimal risk involved. There is a small chance the needle will cause bleeding, a bruise, or an infection
- Discomfort from vestibule biopsies (this is optional)
 - A vestibule biopsy is not from a zone that produces hypertrophied scars, and from our prior experience patients grade the experience as painless, due to topical lidocaine followed by injected lidocaine preparation, with minor pain as they heal.

The subjects in this study will have been screened to be postmenopausal in hormone status, and therefore there will be no risk of pregnancy.

Study Drug:

- All medicines may cause side effects, but many people have no side effects or minor side effects. You may have some side effects we do not expect because we are still learning about estradiol vaginal cream applied to the vulvar vestibule.

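### Exclusion 6 waives lidocaine allergy for the reference women, although the only biopsy preparation the protocol describes uses lidocaine

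*Combined protocol and SAP*

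**What the plan says.** All references are to the combined protocol and SAP.

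- **Section 5, Exclusion Criteria, item 6:** "Allergy to local estrogen products or lidocaine numbing agents", followed by an asterisk. The footnote to the starred criteria is "n/a for reference group".
- **Section 5, Number of Subjects:** the 5 reference women complete the entry questionnaire and "have a 4mm mucosal biopsy in the right or left vestibule adjacent to a Bartholin's duct orifice". Nothing is said there about anaesthesia.
- **Section 9, Duration of Participation:** "Participation for reference group subjects will last the duration of Visit 1".
- **Section 9, Visit 1:** the biopsy item is headed "Vulvar biopsy (for those subjects enrolling in the sub-study" and describes a 4 mm punch at the 4 or 8 o'clock position beside a Bartholin duct orifice, taken "after the zone has been pretreated with topical 5% lidocaine ointment for 10 minutes".
- **Section 15, Risks to Subjects:** vestibule biopsies are said, on prior experience, to be graded painless "due to topical lidocaine followed by injected lidocaine preparation". The text does not separate sub-study from reference women.
- **Section 12:** the reference women are there to supply biopsy specimens for an exploratory aim (n=5), and the protocol says they are not strictly controls.

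**The concern.** An eligibility waiver should remove only criteria that do not matter for the group concerned. Here one asterisk removes two allergies of different relevance. Estrogen allergy does not matter for a woman who gets no cream. Lidocaine allergy does matter if her one invasive procedure is prepared with lidocaine.

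A site applying the list literally would record lidocaine allergy as not applicable for a reference candidate and could go on to the biopsy. What is at stake is participant safety in a group with no prospect of treatment benefit, whose written protection on this point is weaker than that of the 50 women with dyspareunia. No estimate, test or power figure depends on it.

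**Working it through.** No arithmetic is needed to establish the point. It is a check of one part of the protocol against another.

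1. **What does the asterisk cover?** It stands at the end of exclusion 6. If it governs the whole criterion, lidocaine allergy is waived. If it governs only the nearest phrase, lidocaine allergy is still waived, because that phrase is the lidocaine one. Exclusion 2 shows that a criterion can be starred in part: there the asterisk sits mid-sentence, after the swab-test half. Exclusion 6 was not divided in that way.

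2. **Does the waiver fit the estrogen half?** Yes. Reference women attend Visit 1 only and are not followed up, so they never use the cream.

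3. **Does it fit the lidocaine half?** The two biopsy descriptions compare as follows.

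| Feature | Reference biopsy (section 5) | Sub-study biopsy (section 9, Visit 1) |
|---|---|---|
| Size | 4 mm | 4 mm |
| Site | Right or left vestibule, beside a Bartholin's duct orifice | 4 or 8 o'clock, beside a Bartholin duct orifice |
| Visit | Visit 1 | Visit 1 or 2 (baseline sample) |
| Preparation | Not stated | Topical lidocaine ointment |

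   Section 15 adds injected lidocaine after topical, for vestibule biopsies in general. No preparation without lidocaine appears anywhere. The natural inference is that the reference biopsy would be prepared with lidocaine too.

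4. **Does another criterion exclude the allergic woman?** No other inclusion or exclusion criterion mentions lidocaine allergy. The unstarred half of exclusion 2 concerns tenderness that lidocaine fails to relieve, which is a different matter and arises only if tenderness is found.

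5. **Is there another safeguard?** Visit 1 includes a medical, surgical and medication history, and section 8 has a nurse practitioner or study physician perform the screening examination. An allergy might come to light there. But allergy is not named in the history item, and the purpose of that examination is to confirm the criteria as written, which mark this one not applicable for reference women.

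6. **How many women?** At most 5 of 55 (5/55 = 9%), and in practice only those who are allergic. The protocol gives no prevalence of lidocaine allergy, so no expected count can be derived from it.

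**The case against.** The strongest reply is that the protocol never states that reference biopsies are done under lidocaine. Section 5 is silent on anaesthesia, and the lidocaine step in section 9 is labelled for the sub-study, whose members are biopsied before and after treatment. Reference women are not among them. This stands, and it is why the link is presented here as an inference. It does not remove the problem: if the section 9 preparation does not apply to reference women, the protocol gives no preparation for their biopsy at all, and that also needs a sentence.

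A reader might go further and infer that all five women would receive two lidocaine exposures, topical and injected. The documents do not support that. The section 9 procedure is topical only. The injection appears only in the risk text, as part of a remark about prior experience. Adding the two together joins a step written for another group to a description of past patients.

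It can also be said that eligible does not mean exposed. The asterisk removes an exclusion; it does not direct staff to give lidocaine to an allergic woman, and a clinician may well learn of the allergy first. That is a fair partial safeguard, but it is not a written exclusion.

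Finally, part of the waiver may have had a reason. For the women with dyspareunia, lidocaine also serves the tenderness test and the ultrasound preparation, and neither is clearly needed in women without pain. The protocol does not give this reason, and it leaves the biopsy unaddressed.

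**Conclusion.** The point holds as an inconsistency between an eligibility waiver and the biopsy procedure. As written, lidocaine allergy does not exclude a reference woman, and the only biopsy preparation described would expose her to lidocaine.

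This rests on two assumptions: that the reference biopsy is prepared like the sub-study biopsy, which is inferred and not stated; and that the eligibility forms follow the printed criteria. The phone screen form is mentioned but is not part of the documents, so what it asks about allergy is unknown.

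The severity is moderate. It is a safety matter with a very cheap remedy, but it concerns no more than five exploratory participants and an event that should be rare. Randomisation, endpoints, power and analysis are not affected, so it would be wrong to treat it as a flaw in the trial's comparison or as a must-fix.

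**What to change.** Reconcile exclusion 6 and its footnote with the reference-biopsy description in section 5, the Visit 1 biopsy item in section 9 and the biopsy risk text in section 15. There are two ways to do this:

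- split exclusion 6 into separate estrogen-allergy and lidocaine-allergy items, and attach the reference-group waiver to the estrogen item only; or
- keep the waiver as it is and state, for the reference biopsy, a preparation that is consistent with it.

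The first is the simpler edit. The choice belongs to the investigator and the sponsor. Either way, section 9 should say whether its biopsy item covers the reference women, and the eligibility checklist should be brought into line with the result.

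The cost of the first option is a one-line amendment and a checklist edit, with no added procedure. The downside is that a rare reference candidate may be lost.

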The standard regimen for local estrogen supplementation was approved by the FDA for the primary outcome of vaginal atrophy (Suckling 2006). The regimen that lowers pH and converts an immature maturation index to a mature index is the following: two weeks of daily intravaginal estrogen by any of several low-dose products such as cream or tablets. Once the atrophy is corrected, the maintenance regimen doses the same estrogen product twice weekly. The vaginal mucosa responds quite quickly to this dosing schedule of estrogen. After 2005 the FDA began requiring that products correct more than atrophy. They required that products also assess "the most bothersome symptom" (Ettinger, 2008). These symptoms could include irritation, itching or a sense of dryness and perhaps dyspareunia. No studies to date have assessed the effect of estrogen on pain at the vestibule, which is the likely site of tenderness, nor what dosing regimen is required to address pain instead of atrophy.

Urinary symptoms are part of the Genitourinary Syndrome of Menopause. For this reason, we are collaborating with our urogynecology colleagues to explore some bladder issues that our cohorts may exhibit. Evolving research has pointed to the role that microorganisms play, and hormone status has a strong relationship to urinary tract health. It has become possible to evaluate microbial communities with techniques that are culture-independent using a DNA-based approach (Brubaker, 2015). From locally collected swabs from the vestibule and vagina we will characterize the resident microbial community using a DNA-based approach by amplifying the bacterial 16S ribosomal RNA (rRNA) gene via PCR. We will perform next-generation sequencing using Illumina MiSeq (Metzker 2010). This will be analyzed with the help of the urogynecology biostatistician using QIIME bioinformatics software.

Because dyspareunia is a pain condition whose provocation is vaginal intercourse, it has been important to have a proxy maneuver that does not involve a sexual partner. Foster and colleagues tested and validated the Tampon Test using a hygiene item with which most women have had experience (Foster, 2009). It was validated in pre-menopausal women with dyspareunia and Goetsch used it in her postmenopause study (Goetsch, 2015). Not all subjects had tampon pain despite all having intercourse pain. It is the only proxy test accepted by experts in vulvar pain.

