The study will include 50 subjects affected by dyspareunia and 5 reference cases (Total N=55). We estimate a need to screen 60 women in order to enroll 50 patients and we arrived at this estimate using the following considerations. We assume that all potential subjects who pass the phone screening and come for a screening examination having the complaint of postmenopausal dyspareunia will be found to have tenderness in the vulvar vestibule, as found in 100% of screened women in our previous study to locate the site of genital tenderness in a similar population (Goetsch, 2014). The prediction of how many women may be eliminated at screening comes from cautions regarding uterine issues. Although prior studies have indicated that use of local estrogen is without risk of stimulation to the uterus, we will be studying doses to an anatomic area with no prior data on absorption. We therefore feel it is important to screen candidates with a uterus to ensure that they enter the study with no evidence of thickening of the uterine lining, which can predispose to endometrial cancer. In women with a uterus, we will assess the width of endometrial stripes by transvaginal ultrasound. A 2011 British study of transvaginal endometrial screening found that 10-20% of asymptomatic women had a stripe width of 5 or more. (Jacobs, 2011) Those with a stripe ≥5mm will be excluded. The Oregon obesity prevalence is 29% (StateofObesity.org), defining a population at increased risk for endometrial thickening from adipose-related estrogen unopposed by any progestin. From a 2012 publication reporting the number of women in a Kaiser Permanente Northwest population who have had hysterectomies, we hypothesize that 26% of women screened will not have an intact uterus. (Lacie, 2012) Calculating the excess screens needed due to thickened endometrium in obese women and considering the proportion likely to have had hysterectomies, an estimated 60 women will be screened to enroll 50 subjects. All will be in the OHSU cohort.

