Data will be entered into REDCap from paper charting and/or via direct REDCap entry by study participants using laptop or iPad. Serum specimens will be stored in freezers in WHRU and sent for batched analysis at the Oregon National Primate Research Center (ONPRC). Ultrasound data and photos will be stored electronically and in charts in WHRU and REDCap.

Serum specimens will be stored in WHRU freezers and then batch shipped to the ONPRC for analysis. Biopsy specimens will be preserved in formalin and batched for staining and analysis by [name] in the OHSU pathology department. Data will be stored until the study has been published and then archived to Iron Mountain for indefinite storage. Any remaining serum or biopsy specimens will be stored for one year beyond completion of the study or until advised to discard by the PI.

Batched serum specimens will be sent to the ONPRC lab on dry ice. Swabs with samplings from vestibules and vaginas will be frozen and stored for later sequencing and analysis.

b. Sharing of Results with Subjects

Subjects with a uterus will undergo a screening pelvic ultrasound and an exit pelvic ultrasound to assess the endometrial stripe. If at screening the stripe is ≥5mm, they will be advised to consult with their personal gynecologist to consider a progestin challenge test and they will be excluded from study participation.

If at study exit the stripe is ≥5mm, they will be advised to consider oral Norethindrone for 10 days to see if any bleeding is provoked and follow-up with their personal gynecologist. In addition, they will be advised to consult with their personal gynecologist for advice on monitoring the endometrium in the future should they wish to continue using estrogen cream. It is not expected that use of study drug will stimulate endometrial thickening.

Serum β -estradiol results will not be shared with the participants.

c. Data and Specimen Banking

Specimens and data may be placed in the WHRU repository for future research. No genetic research will be done.

Blood samples will be sent for analysis to the ONPRC. Tissue biopsies will be analyzed and then stored by the Department of Pathology, OHSU. Swabs collecting material from vestibule and vagina will be frozen and stored for later sequencing and analysis as batched samples.

12. Data Analysis

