- The estrogen cream used in the study is similar to the FDA approved estradiol vaginal cream (ESTRACE). When estrogen cream is placed deep in the vagina in the same dose as the study cream, absorption is low and for most women blood levels remain the same as for those not using estrogen cream. If absorption takes place, side effects may include:
- Most Common:
 - Headache (13%)
- Less Common (1-10%):
 - Hot flushes
 - Breast tenderness
 - Vaginal infection (yeast infection, bacterial infection)

- Vaginal pain/discomfort
- Vaginal spotting
- Gastrointestinal complaints (abdominal pain, nausea, diarrhea)
- Urinary tract infection
- Hair loss
- Insomnia
- Anxiety
- Dizziness
- Changes in libido
- Back and joint pain
- Respiratory tract infection
- Discoloration of the skin
- Rare but Serious Side Effects (<1%)*
 - Endometrial cancer
 - Estrogen therapy may cause the lining of the uterus to grow and can increase the risk of uterine cancer. Because the amount of estrogen absorbed is low when using topical estrogen cream, the risk for uterine cancer is lower than when taking oral estrogen. You will have pelvic ultrasounds throughout the study to monitor the lining of the uterus.
 - Breast cancer
 - Estrogen therapy is associated with a small increased risk of breast cancer.
 - Cardiovascular disease
 - Estrogen therapy has been shown to increase the risk of heart disease including heart attack, stroke, and serious blood clots in some women.
 - Dementia
 - An increased risk of developing probable dementia in postmenopausal women 65 years of age or older has been reported in women receiving oral estrogen alone or estrogen combined with progestins.
 - As with any drug, allergic reactions may occur due to the study drug. These may range from mild to severe, can be life-threatening/fatal and include hives, difficulty breathing, and swelling of your face, lips, tongue, or throat. You should seek emergency medical treatment should you experience an allergic reaction.

b. Potential Benefits to Subjects

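### No entry criterion covers a previous venous thromboembolism, stroke or heart attack, and exclusion 7 counts a caution about estrogen only when the reason was cancer

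*Combined protocol and SAP*

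**What the plan says.** **Entry criteria (section 5).** Exclusion 7 bars previous estrogen-receptor-positive breast cancer, previous endometrial cancer, and any woman who "has been cautioned about estrogen because of any other cancer". The other two drug-safety exclusions are allergy (6) and an endometrial thickness of 5 mm or more (8). Investigator discretion appears only in inclusion 4, for the length of the partnership.

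**Risks (section 15a, Study Drug).** The side-effect list is introduced as what may happen if the drug is absorbed. Its rare but serious part includes: "Estrogen therapy has been shown to increase the risk of heart disease including heart attack, stroke, and serious blood clots in some women". Just before the list, the protocol says that when cream is placed deep in the vagina at the study dose, "absorption is low and for most women blood levels remain the same as for those not using estrogen cream".

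**Absorption (section 5, Number of Subjects).** The reason given for screening the uterus is that "we will be studying doses to an anatomic area with no prior data on absorption".

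**Safeguards (sections 8, 9, 11 and 14).** Medical history is taken at Visit 1 and updated at Visit 2. A nurse practitioner or physician examines each woman against the listed criteria. History and possible drug symptoms are reviewed at weeks 4, 8 and 12. On serum estradiol: "Serum specimens will be stored in freezers in WHRU and sent for batched analysis"; results are not given to participants. Section 14 refers to a separate DSMP.

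**The concern.** All 50 treated women are to apply estradiol nightly for three months to a site whose absorption the trial itself sets out to measure. A woman who has already had a clot, stroke or heart attack has had one of the events that the protocol lists as a serious estrogen risk. If she otherwise qualifies, the written criteria admit her. A woman whose clinician told her to avoid estrogen after a clot is also admitted, because exclusion 7 limits such advice to cancer.

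What is at stake is the safety of individual participants, not the validity of the analysis. The natural place to settle the question is before the first dose, and the criteria leave it to the judgment of whoever takes the history.

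**Working it through.** No power or sample-size figure bears on this point. The check is a count, a comparison of sections, and a small sum for the cost of the fix.

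**Step 1. Count the criteria.** Inclusion has 9 items (item 2, with its five alternative definitions of menopause, counts as one). Exclusion has 9. Total 9 + 9 = 18.

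**Step 2. Read each for a vascular history.**
- Inclusion covers age, menopausal status, onset and duration of dyspareunia, partnership, six months without estrogen, and willingness to follow the study procedures.
- Exclusion covers pelvic pain, the swab and lidocaine tests, partner dysfunction, pelvic floor or bladder tenderness, constant vulvar burning, allergy, cancer, endometrial thickness and vulvovaginitis.
- Criteria naming thromboembolism, stroke, heart attack or cardiovascular disease: 0 of 18.
- Criteria acting on a caution about estrogen: 1 of 18 (exclusion 7), for cancer only.
- General contraindication or medical-discretion clauses: none.

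**Step 3. Look for another bar to entry.** Section 8 says the screening examination verifies the listed criteria. Section 9 (Visit 1) lets randomization proceed once staff have confirmed eligibility. History is collected, but no written rule acts on a vascular finding.

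**Step 4. Compare the rare but serious risks in section 15a with the criteria.**

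| Risk listed | Matching criterion |
|---|---|
| Endometrial cancer | Exclusion 7 (history); exclusion 8 (thickness) |
| Breast cancer | Exclusion 7 (receptor-positive) |
| Allergic reaction | Exclusion 6 |
| Dementia | None, but the protocol says it "has been reported in women receiving oral estrogen alone or estrogen combined with progestins", which is not the study drug |
| Heart attack, stroke, serious clots | None; stated for estrogen therapy generally |

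**Step 5. Compare with the sponsor's own reasoning.** Section 5 accepts that prior studies of local estrogen found no stimulation of the uterus, yet excludes a thickened endometrium because the site is unstudied. Section 3 cites a professional opinion that the data do not show higher breast cancer recurrence with local estrogen, yet exclusion 7 bars receptor-positive disease. In both places the plan is cautious despite reassuring vaginal data. It gives no reason for treating vascular history differently.

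**Step 6. Cost in screening.** The plan expects 60 clinic screens for 50 enrolled. That figure already carries an allowance, described as "Calculating the excess screens needed due to thickened endometrium in obese women", so no spare capacity is assumed. Let p be the share of candidates newly excluded. The documents give no rate, so 1% to 5% is an assumption. If all are found in clinic, screens = 60 / (1 − p):
- p = 1%: 60 / 0.99 = 60.6, so 61
- p = 2%: 60 / 0.98 = 61.2, so 62
- p = 5%: 60 / 0.95 = 63.2, so 64

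If all are found by phone, the number stays at 60.

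**The case against.** **The risk list is conditional.** The vascular item sits under a lead-in that applies only if the drug is absorbed, next to a statement that absorption is low at this dose. This stands, and it limits the size of the concern. It does not remove it, because the reassurance concerns deep vaginal placement and section 5 says the vestibule has no data. The heading of the serious-risk list also carries an asterisk whose note is absent from the supplied text and may qualify the list.

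**Not every listed risk needs a history exclusion.** True; no rule requires it. The comparison in step 4 shows only where the plan is silent, not that it breaks a standard. Which histories to exclude for a low-dose topical drug is a clinical judgment.

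**There are other safeguards.** History at Visits 1 and 2, examination by a clinician, and reviews at weeks 4, 8 and 12 are real protections, and a clinician may well decline such a woman. But the protocol gives no written basis for doing so, and the first scheduled symptom review comes after about four weeks of dosing. Batched serum results cannot be counted on to guide an individual's dosing.

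**Documents are missing.** The phone screen form may already ask about these events, and the DSMP may address them. The gap is shown in the written criteria only.

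**Stronger readings that do not hold.** A reader might infer that nightly use means a proportionally higher systemic exposure than the standard twice-weekly maintenance schedule. The documents do not support this: a count of applications is not a dose, and section 3 gives no microgram amount for the standard schedule. A reader might also infer that enrolling such a woman is likely. No prevalence is given, and the chance of enrolling her would in any case not be a chance of harm.

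**Conclusion.** The point holds as a gap in the written criteria: 0 of 18 cover a previous venous thromboembolism, stroke or heart attack, and the one criterion about a caution against estrogen is limited to cancer. If the plan is followed as written, a woman with such a history who meets the other criteria would be dosed.

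It is worth considering rather than serious. The added risk is probably small, given the protocol's own account of vaginal absorption, and it cannot be calculated from the documents. Nothing in them shows that this dose and route raise vascular risk or that anyone was harmed. The conclusion assumes that the unsupplied phone screen form and DSMP do not already exclude these women. It concerns only the 50 treated women; the 5 reference women receive no study drug.

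**What to change.** Add one exclusion: 'Previous venous thromboembolism, stroke or heart attack', marked as not applicable to the reference group. Leave exclusion 7 as it is, so that its cancer wording continues to apply to both groups. A separate clause about being cautioned against estrogen because of these events is largely redundant once the event itself excludes. The investigator should confirm the list, and the phone screen form should be checked to see that it asks about the three events. If the sponsor prefers to keep these women eligible, a sentence saying so and why would also settle the matter.

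Cost: a one-line amendment and a form check. A few candidates are lost. Clinic screens may rise slightly above 60 (61 to 64 under the assumed 1% to 5%) or stay at 60 if the phone screen finds them all. The 50 enrolled, and so the power, are unchanged.
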